5.0 Inclusion and Exclusion Criteria/Study Population

Screening Procedures. Prospective subjects (self-referred via flyers, e-mail announcements, and Catalyst advertisements) will be interviewed by the research team over the phone. Questions asked during this phone interview will focus on chronic (and current) medical problems, seizure history, medications, psychiatric disorders, substance abuse, magnetic resonance imaging eligibility and pain history. The inclusion/exclusion criteria will be used to screen-out participants with conditions that might interfere with or confound the research, or that might render participants vulnerable to potentially negative effects of the

laboratory pain procedures. A copy of the screening form is uploaded to the eIRB website. If the participant qualifies for the study and wishes to proceed, then he or she will be invited to a screening visit that will take place in a quiet office in the Institute of Psychiatry. The research procedures, risks and benefits will be explained during this visit. After providing written informed consent to participate, if the participant is female, then she will also receive a pregnancy test. Participants will be paid **\$30** for participating in the screening procedure. Participants meeting inclusion criteria will be invited to participate in the laboratory investigation. If they choose to participate, they will be paid **\$120** for Visit 2 scanning session and **\$120** for Visit 3 scanning session for a total of **\$270**.

Selection Criteria. Participants must meet the following criteria: (1) 18-45 years of age, (2) no seizure history (individual or family), (3) no history of depression, (4) no hospitalizations or surgeries in the previous 6 months, (5) not currently experiencing pain, (6) no history of chronic pain, (7) no metal implants or objects (e.g. pacemakers, metal plates, wires), (8) not pregnant, (9) no alcohol dependence (10) no illicit drug use in the previous 6 months, (11) no known allergy to capsaicin, (12) no history of brain surgery or brain lesions, (13) no history of loss of consciousness (greater than 15 min), (14) no stimulants or medications that lower seizure threshold.

6.0 Number of Subjects – 35

7.0 Setting

The initial screening, interview, and structural scan (Visit 1) will be on the Center for Biomedical Imaging at [name]. For Visit 2 and 3, the Brainsight targeting will occur on at the Brain Stimulation Lab on the 5th floor of the Institute of Psychiatry. The LIFUP-MRI scanning will be done at [name]

8.0 Recruitment Methods

We will use flyers and word of mouth and email to recruit these healthy volunteers.

9.0 Consent Process

Subjects will be phone screened and then scheduled for an interview on the [name]. There they will read the informed consent and the investigators will answer questions.

10.0 Study Design/Methods

10.1. Study Design. Twenty healthy volunteers between 18-65 years of age without history of depression or chronic pain will be recruited to participate in this sham-controlled, double-blind crossover study, all within one session within the MRI scanner. All participants will receive 10 minutes of sham LIFUP, 20 minutes of rest, and 10 minutes of real LIFUP within the MRI scanner using the BXPulsar 1001, Brainsonix Inc. The order will be counterbalanced. The duration of the LIFUP analgesia and BOLD effects will be determined.

10.2. Behavioral Measures. We will begin baseline pain assessments by administering cutaneous hot and cold stimuli via the Medoc Pathway System (Medoc, Durham, NC) using a 30 x 30 mm ATS thermode. There will be two behavioral measures: quantitative sensory testing (QST) on untreated skin and blocks of pain on capsaicin-treated skin.

QST will be done using method of limits testing on the thenar eminence of the right hand. A program will be set up to administer 10 hot stimuli with random durations between each trial. The ATS thermode begins at 32°C and increases by 0.5°C per second. Participants will be asked to press a button in order to signify three different measures: (1) sensory threshold, or the temperature at which the stimulus becomes noticeable, (2) pain threshold, or the temperature at which the stimulus becomes painful, and (3) pain tolerance, or the temperature at which the stimulus becomes too painful to tolerate. Measuring these thresholds will yield information about

A β , A δ , and C fibers, respectively. The device will be set to stop heating at 51.5° C and stop cooling at 0° C to avoid tissue damage. These ten trials will be performed once before and once after each scanning block, either with thalamic LIFUP or 'fake' thalamic LIFUP.

Blocks of pain will be administered with an adaptation of an established heat/capsaicin model (27). First, 1% capsaicin cream will be applied to a 40 x 40 mm region of skin 12 cm away from the wrist on the right volar forearm. After 30 minutes, the capsaicin cream will be cleaned off and cutaneous heat stimuli will be applied via the Medoc Pathway System using a 30 x 30 mm ATS thermode. Pain ratings will be assessed by administering 22 s blocks of pain at a temperature that each participant reports at baseline to be 7 out of 10 on a pain visual analog scale. This temperature, individualized for each participant at baseline using the PEST procedure, will be administered throughout the experiment. Studies have shown that stimuli rated as 7 out of 10 produce highly reproducible results in terms of pain ratings and fMRI activation without posing significant risk to participants (28). The device will be set to stop heating at 51.5° C to avoid tissue damage. After each heating trial, participants will rate the intensity of the pain from 1-10. The temperature rated as "7 out of 10" at baseline will be administered 12 times during the baseline scan, 12 times during the scan following sham LIFUP and 12 times during the scan following real LIFUP. These procedures have been used previously in IRB-approved studies.

10.3. Magnetic Resonance Imaging (MRI). A Siemens 3T Trio MRI scanner will be used for imaging. After QST testing, the MR compatible ATS thermode will be placed on the capsaicin-treated right volar forearm. Participants will undergo standard high-resolution anatomical scans prior to undergoing functional scans during which 22 second blocks of heat will alternate with 22 second blocks of rest. These heat stimuli were previously rated as "7 out of 10" in intensity during baseline testing. Each fMRI scan will involve 12 pain/rest blocks. At the end of the functional scan, each participant will rate the intensity of the pain that they experienced. The functional pain/rest scan will be repeated three separate times throughout the experiment: (1) at baseline, (2) after 20 min of sham LIFUP, and (3) after 20 min of real LIFUP. A short interleaved LIFUP-fMRI scan will be performed immediately before the pain/rest block scans after sham LIFUP and real LIFUP. During these sessions, the LIFUP machine will fire single pulses at 1Hz frequency. A TR delay will be used to minimize LIFUP-induced destruction of acquired scan data. E-Prime software will be used to trigger LIFUP pulses and coordinate them with scanner TR delays. The purpose of the interleaved LIFUP-fMRI sequence is to examine how LIFUP affects BOLD signal changes in real time.

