When I first proposed to do TMS in the scanner over 20 years ago the MUSC IRB required that I be the first test subject, and report back. I did that and am prepared to do that here if that is what is needed. I think this LIFUP is as safe as diagnostic ultrasound, and has enormous research and clinical potential.)

Specific Aims.

- Aim 1.** Test the safety and feasibility of LIFUP to thalamus in healthy volunteers.
- Aim 2.** Characterize the time course and magnitude of thalamic LIFUP-induced analgesia.
- Aim 3.** Identify the brain circuitry (BOLD activity) that thalamic LIFUP changes during induced pain.

Hypothesis.

The anterior nuclei of the thalamus in addition to periaqueductal gray (PAG) and rostral ventromedial medulla (RVM) are integral regions of a supraspinal opioidergic structure that regulate pain perception (4-8). With the capability to influence deep neurological tissues, low intensity frequency ultrasound pulsation can likely modulate this circuit and induce analgesia. LIFUP deep brain modulation is achieved by induction of focused mechanical waveforms that traverse the cranium and underlying brain tissue (19). The low frequency of the ultrasonic wave consequently alters neuronal transmission and causes action potential variations through mechanical means, rather than thermal (20). The purpose of this study is to examine whether stimulation of the anterior nuclei of the thalamus via LIFUP induces analgesia. **We hypothesize that suppression of the anterior nuclei of the thalamus will induce a temporary increase**

in pain tolerance. Moreover, the behavioral changes in pain will correlate with specific regional BOLD changes during pain.

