Researchers have examined the effects of LIFUP in preclinical and clinical settings, confirming its ability to safely stimulate neural tissue⁽¹¹⁻¹⁴⁾, proposing cellular mechanisms for its efficacy⁽¹³⁻¹⁹⁾, and now using LIFUP in human patients⁽²⁰⁾. Monti et al. (2016) described a case study in which they used LIFUP to stimulate a comatose patient's thalamus.⁽²⁰⁾ Two pre-LIFUP assessments rated the patient as being in minimally conscious state (MCS). After sonication, the patient recovered motor and oromotor functions the next day, advancing to full language comprehension and communication by nodding and shaking his head. Five days post-LIFUP, the patient attempted to walk. While this study was neither blinded nor sham-controlled, the first application of therapeutic LIFUP in a human patient was encouraging and we expect more therapeutic applications of LIFUP and potential clinical trials in the future. If LIFUP continues to show clinical potential, it has the potential to supplant the role of DBS without the need for surgery. The key barrier to LIFUP replacing DBS for clinical applications is that by and large, DBS is used in a manner where the device is inserted and turned constantly on without attempting to fundamentally change circuit dynamics or behavior so that you could remove the device. Obviously, patients cannot permanently wear a LIFUP helmet. However, to the degree that we learn how to stimulate in ways that permanently change circuit behavior (LTD or LTP) without ablation, we may be able to substitute several sessions of LIFUP that can train and rewire the brain instead of permanently implanting hardware. LIFUP can certainly stimulate deep and focal and noninvasively and thus may be a key next step in the field of brain stimulation.

Information on the intervention to be studied.

We will be using the Brainsonix Low intensity focused ultrasound pulsation device. (BX Pulsar 1001). Please see the manufacturers description (Technical Summary) along with appendixes about the actual safety of the device itself.

FDA Status of the BX Pulsar 1001 device.

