12.0 Data Management

The behavioral pain measures will be examined using a repeated measures ANOVA with time and condition (LIFUP, sham) as between group variables. These will be paired data within each subject.

Justification of Sample Size: Prior studies by our group using this same paradigm have shown differences in pain intensity with prefrontal TMS, or blocking of opiates. (29)

Consent procedures will be carried out within a private room inside the IOP. Data acquisition will be performed within the MUSC CBI research scanner at [name] The data will not be labeled with identifiable information. Participants will be identified on all research records solely by a number, ensuring confidentiality of all data. Any information that is obtained in connection with this study and that could identify the participants will remain confidential and will not be released or disclosed without their further consent, except as specifically required by law. If the results of this research are presented at scientific meetings, participant identity will not be

disclosed. All conversations with participants will take place behind closed doors in front of only the participant and designated caregivers, family, or friends.

Any imaging or other research data will be stored in a de-identified manner.

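### The 20-minute rest between real and sham LIFUP is not justified, and the planned analysis would not show carry-over, which can dilute the real-minus-sham contrast in pain-block ratings and BOLD

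*Combined protocol and SAP*

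**What the plan says.** Section 10.1 describes a "sham-controlled, double-blind crossover study, all within one session within the MRI scanner". The schedule is: "All participants will receive 10 minutes of sham LIFUP, 20 minutes of rest, and 10 minutes of real LIFUP". On order it says "The order will be counterbalanced", and on persistence "The duration of the LIFUP analgesia and BOLD effects will be determined". Aim 2 in section 1.0 is to "Characterize the time course and magnitude of thalamic LIFUP-induced analgesia".

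The measures have different baselines:

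- **Pain-block ratings and BOLD** (sections 10.2 and 10.3): one baseline scan, one scan after sham and one after real. There is no fresh baseline before the second condition.
- **QST** (section 10.2): "These ten trials will be performed once before and once after each scanning block". A measurement before the second condition therefore exists.

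The behavioural analysis in section 12.0 is a "repeated measures ANOVA with time and condition (LIFUP, sham") with no mention of period, sequence or carry-over.

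Two features of the schedule are inconsistent. Sections 5.0 and 7.0 describe scanning at Visit 2 and Visit 3, whereas sections 10.1 and 16.0 describe one session or one scan. Stimulation lasts 10 minutes per condition in section 10.1 and 20 minutes in section 10.3.

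**The concern.** A crossover estimates the real-minus-sham difference cleanly only if the effect of real LIFUP has gone by the time the sham condition is measured. The pain blocks are rated in a scan that follows stimulation, so the design relies on the effect outlasting sonication by at least the length of that scan. It then relies on the effect having gone by the sham scan, perhaps half an hour to an hour later. No evidence is offered that the duration falls in that window, and duration is one of the things the study sets out to learn.

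Counterbalancing does not remove carry-over. It confines it to the real-first participants, whose sham scan would be taken on whatever remains of the real effect. If the residue acts in the same direction as the effect, the pooled contrast for pain-block ratings and BOLD shrinks toward zero, most of all when the effect is long-lasting. A small or null result on these measures could then reflect either no effect or a persistent one, and nothing in the planned analysis would help to tell them apart.

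**Working it through.** The plan gives no effect size, SD, power or carry-over figure, so there is no stated figure to reproduce. What follows is illustrative.

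**Post-only measures (pain-block ratings, BOLD).** Let E be the true effect and c the fraction still present at the sham scan in real-first participants, in the same direction.

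- Sham-first: real minus sham = E.
- Real-first: real minus sham = E - cE.
- Half in each order: average = E(1 - c/2). At c = 1 this is 0.5E, the floor.

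**Gap between the two scans in real-first participants.** Section 10.3 gives 12 blocks of 22 s heat plus 22 s rest: 12 x 44 s = 8.8 min. Section 10.2 gives ten ramps from 32 to at most 51.5 °C at 0.5 °C/s: 10 x 39 s = 6.5 min of heating at most per QST set. The protocol does not say whether these fall inside the rest. With 10-minute stimulation:

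- scan and QST inside the rest: 20 + 10 = 30 min;
- scan outside: 8.8 + 20 + 10 = 38.8 min;
- scan and two QST sets outside: 8.8 + 13 + 20 + 10 = 51.8 min.

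**Effect retained**, assuming exponential decay, c = 0.5^(gap/half-life):

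| Assumed half-life (min) | Gap 30 | Gap 38.8 | Gap 51.8 |
|---|---|---|---|
| 10 | 94% | 97% | 99% |
| 20 | 82% | 87% | 92% |
| 40 | 70% | 74% | 80% |
| 80 | 61% | 64% | 68% |
| 160 | 56% | 58% | 60% |

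Example: half-life 40, gap 30 gives c = 0.5^0.75 = 0.59 and 1 - 0.59/2 = 0.70. The 20-minute stimulation of section 10.3 would add 10 min to each gap; at 40 and 61.8 min the range is 58% to 99%. The short interleaved scan has no stated length and is not counted.

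**Cost in power.** Assume a paired t-test, two-sided 0.05, with the effect set to give 80% power without carry-over (standardised paired effect 0.66 for N = 20, 0.49 for N = 35). Both sample sizes appear in the protocol. Power falls to about 69%, 56%, 42% and 29% at c = 0.25, 0.5, 0.75 and 1, the same to within a point for either N.

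**Pre/post QST change.** Let c1 and c2 be the fractions left before and after the sham block in real-first participants, with c2 < c1. Their sham change is E(c2 - c1), so their contrast is E(1 + c1 - c2). Sham-first participants give E. The average is E[1 + (c1 - c2)/2], which is not below E. For example, take a half-life of 40 min, with the pre-sham QST 6.5 + 20 = 26.5 min and the post-sham QST 51.8 min after the post-real one. Then c1 = 0.63, c2 = 0.41 and the multiplier is 1.11.

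**Can carry-over be detected?** For N = 20 (10 per order) and the effect of 0.66, compare the change from the pre-first-block to the pre-second-block QST between orders. Taking the SD of that change as equal to the SD of the paired difference, power is about 29% at c = 1 and 11% at c = 0.5. A test on subject sums has 8% to 18% at c = 1, for within-subject correlations of 0.8 down to 0.3.

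**The case against.** The strongest reply is that the documents expect a short effect. Section 1.0 hypothesises a temporary rise in pain tolerance, and section 3.0 cites reversible physiological effects. With a half-life of 10 minutes, only 1% to 6% of the effect is lost. This stands as a reason not to assume serious dilution. It does not supply a duration or justify 20 minutes. Section 1.0 also mentions healthy-adult thalamus data in an attached poster, which is not among the documents and may bear on the question.

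A reader might infer several stronger things that the documents do not support:

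- **That carry-over cannot be recognised.** QST before each block and two treatment orders make a check possible. The point is that none is planned, and that its power would be low.
- **That every pain measure is diluted.** Pre/post QST change is not, and pain tolerance, the variable in the hypothesis, is a QST measure. Section 12.0 does not say whether its time factor means pre/post.
- **That the pooled estimate is a lower bound.** This fails for QST change and for opposite-direction carry-over. Section 3.0 reports both excitation and inhibition, and section 4.1 says only that ratings will be modulated.
- **That the protocol's own evidence shows day-long effects.** The case in section 3.0 ("After sonication, the patient recovered motor and oromotor functions the next day") is one patient in a minimally conscious state, neither blinded nor sham-controlled, with no pain outcome. It illustrates the floor and says little about analgesia in healthy volunteers.
- **That 20 minutes is certainly the only washout.** If the conditions are split over Visits 2 and 3, the interval is longer and the point largely falls away.

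**Conclusion.** The concern holds for section 10.1 as written. The interval between conditions is fixed and unjustified while the duration of the effect is an open question of the study. For pain-block ratings and BOLD, same-direction carry-over with balanced order leaves (1 - c/2) of the effect: about 56% to 99% over the half-lives and gaps assumed here, and never below 50%. The half-lives are assumptions, and the actual loss cannot be computed from the documents. The planned ANOVA would not reveal it, and these measures have no second baseline. For pre/post QST change the bias runs the other way, if at all. The point is worth correcting because the primary pain endpoint, the BOLD endpoint and the magnitude part of Aim 2 draw on these contrasts, and the analysis changes are cheap.

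**What to change.** 1. **Reconcile the text.** Bring the one-session and single-scan wording (sections 10.1, 16.0) into line with scanning Visits 2 and 3 (sections 5.0, 7.0), and the 10-minute with the 20-minute stimulation (sections 10.1, 10.3). State whether the pain scan and QST fall inside the 20-minute rest, and justify the interval between conditions. Cost: wording.
2. **If both conditions stay in one session, model condition, period and sequence explicitly** as a within-subject analysis, with order recorded. This separates period effects and makes an order difference visible; it does not remove carry-over bias. Cost: a few degrees of freedom.
3. **Pre-specify a first-condition-only comparison**, adjusted for the baseline pain scan, as a sensitivity analysis for pain-block ratings and BOLD. It is free of carry-over from the other condition, but it is between-subject and less precise, so it should not replace the main analysis.
4. **Report the QST before the second block against that before the first, by sequence, as description only.** The data are already to be collected. With about 29% power even at complete carry-over (N = 20, assumptions above), a quiet result is no reassurance and must not decide the primary analysis.
5. **State in advance** that a null pooled result on pain-block ratings or BOLD cannot by itself exclude a long-lasting effect. Do not describe the pooled estimate as a lower bound.

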12.1. fMRI Data Analysis: Individual fMRI Data Analysis (first level analysis): The fMRI data will be analyzed blind to LIFUP activation. MR scans will be transferred into ANALYZE format with MRICro (<http://www.sph.sc.edu/comd/orden/mircro.html>) and then further processed in Matlab 7.3 (Mathworks, Sherborn, MA) with Statistical Parametric Mapping software 12 (SPM12, The Wellcome Department of Cognitive Neurology, London, <http://www.fil.ion.bphf.ac.uk>). Default settings were used unless indicated otherwise. All volumes will be realigned to the first volume. After realignment, for all subjects, movement across the 8 minutes scan must be less than 0.5 mm in 3 axes and less than 0.5 degree in 3 orientations. The images will be normalized stereotactically into a standard space with a resolution of 3 mm³ voxels using the averaged functional EPI image – the Montreal Neurological Institute (MNI) EPI template in SPM12. Subsequently, the data will be smoothed with an anisotropic 8 mm³ Gaussian kernel and high-pass filtered (cut-off period=128s). In a first level of statistical analysis, using a boxcar function convolved with the modeled hemodynamic response function as the basic function for the general linear model, we will obtain contrast-maps of the difference between task and rest for each subject. The six head movement parameters will be included as confounds.

Group Data Analysis (the second level analysis): Subject-specific contrasts will be entered into a second-level analysis to obtain a random effect analysis of activation effects across the entire group. The combined group *t* maps will be thresholded at $p \leq 0.05$ corrected for multiple comparisons (family-wise error, FWE) and cluster analyses will be performed with a spatial extent threshold of 5 voxels.

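### Section 10.1 counterbalances the order of sham and real LIFUP but describes no random generation or concealment of that order; 10.3 lists sham before real without qualification, and the analysis has no clear period term

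*Combined protocol and SAP*

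**What the plan says.** Section 10.1 describes a "sham-controlled, double-blind crossover study, all within one session within the MRI scanner". It then states: "All participants will receive 10 minutes of sham LIFUP, 20 minutes of rest, and 10 minutes of real LIFUP". The sentence on order follows directly: "The order will be counterbalanced".

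Section 10.3 says the functional pain scan is repeated three times: "1) at baseline, (2) after 20 min of sham LIFUP, and (3) after 20 min of real LIFUP". Nothing there says that the last two may be reversed. Section 10.2 counts the heat stimuli in the same sequence, "12 times during the scan following sham LIFUP and 12 times during the scan following real LIFUP", but as a tally per scan. (The LIFUP durations in 10.1 and 10.3 also differ. That is a separate matter to reconcile and plays no part here.)

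The word random occurs twice in the methods, neither time about order: stimulus spacing in 10.2 ("administer 10 hot stimuli with random durations between each trial") and the group fMRI model in 12.1 ("to obtain a random effect analysis of activation effects across the entire group").

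For the pain measures, section 12.0 plans a repeated measures ANOVA with time and condition. It calls both between-group variables, although its next sentence says the data are paired within subject. Sequence and period are not named, and time is not defined.

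**The concern.** Two things are at stake.

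**Predictability.** Counterbalancing asks only that the two orders occur about equally often. Strict alternation achieves that, yet anyone who knows the rule and one past order knows all later ones. The primary endpoint (section 4.1) is pain ratings, which participants give on a 1-10 scale after each heat trial (section 10.2). The only blinding procedure described is that fMRI data are analysed without knowledge of LIFUP activation (section 12.1). Nothing described protects the collection of ratings.

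**Drift.** Capsaicin is described as applied once and then cleaned off. One temperature, fixed at baseline, is then given 3 x 12 = 36 times over three scans. Ratings could drift through habituation or fading sensitisation. The documents give no size for this. How much of it reaches the LIFUP-sham comparison depends on the split between the two orders and on whether the analysis models period. The text pins down neither.

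**Working it through.** The plan gives no figure to reproduce: section 12.0 justifies the sample size without alpha, power, effect size or SD. What follows is illustration under stated assumptions.

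**Inputs from the documents.** Number of participants: 20 (section 10.1) or 35 (section 6.0). Two LIFUP conditions per participant. Analysis factors: time and condition.

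**Assumed.** Two-sided alpha 0.05; no carry-over; no true LIFUP effect; period effect of 0.25, 0.5 or 0.75 SD of the within-subject real-minus-sham difference.

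**1. Predictability.**
- Alternation, one order known: 19/20 = 95% or 34/35 = 97% of orders are certain. Average correct guesses by someone who knows the rule and past orders, N = 20: (0.5 + 19)/20 = 97.5%.
- Permuted blocks with the block size known: certain assignments 33% (blocks of 4) and 25% (blocks of 6); best-guess accuracy 71% and 68%.

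The block figures are for fixed, known block sizes. Varying, undisclosed sizes were not computed.

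**2. Bias from drift.** Let d be the change in rating from first to second period without any treatment effect, and q the share of participants who get real LIFUP second. The unadjusted real-minus-sham mean has bias d x (2q - 1).
- Everyone sham then real, q = 1: bias = d (100%).
- 10:10, q = 0.5: bias = 0.
- 14:6, q = 0.7: bias = 0.4d (40%).
- N = 35: 18:17 gives d/35 (about 3%); 24:11 gives 13d/35 (37%).

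An assumed drift of 0.5 or 1.0 rating points would therefore shift the result by 0.5 or 1.0 only under a fixed order, by 0.2 or 0.4 at 14:6, and by nothing at 10:10. Under simple randomisation of 20, a split of 14:6 or worse in either direction has probability 0.115.

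**3. Type I error of the paired t-test** (simulation, 40,000 runs, N = 20):

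| Period effect (SD) | Fixed order, unadjusted | 10:10, unadjusted | 14:6, unadjusted | 10:10 or 14:6, period term |
|---|---|---|---|---|
| 0.25 | 0.19 | 0.044 | 0.065 | 0.051 |
| 0.50 | 0.57 | 0.030 | 0.098 | 0.051 |
| 0.75 | 0.89 | 0.017 | 0.135 | 0.051 |

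The 10:10 column falls below 0.05 because the unmodelled period effect enters the error term. With true variance 1, the expected sample variance is 1 + (20/19) x p², where p is the period effect. At p = 0.5 this is 1 + 1.053 x 0.25 = 1.263, so the SD is overstated by about 12%. The estimate stays unbiased, but precision is lost.

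The adjusted analysis averages the mean difference of the two sequence groups. Period cancels from that average whatever the split. Under a fixed order there is only one sequence group, so no such adjustment is possible.

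**The case against.** The case against is substantial, and several parts of it stand.

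- **A reader might infer that 10.1 itself sets a sham-then-real order.** It does not. The counterbalancing sentence comes straight after the list, so the list reads as naming the conditions. Only the list in 10.3 stands without a qualifier, and that may be loose wording.
- **A reader might infer that order was not randomised, or that alternation is planned.** The text shows neither. A randomised balanced list would also be called counterbalanced. Sections 2.0, 11.0 and 14.0 are absent from the supplied text, which weakens any argument from silence.
- **A reader might infer that LIFUP is confounded with time.** Under equal counterbalancing the average period bias is already zero, with no period term. The full-drift figures apply only if the 10.3 sequence is given to everyone.
- **Alternation does not by itself unblind participants**, who do not ordinarily see each other's orders. The route is through staff who know the rule and an earlier order. Permuted blocks also leave some predictability.
- **Time in the ANOVA might mean period.** It might equally mean before versus after stimulation, and the text does not say.

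What remains is that the stated rule does not exclude a predictable sequence, no concealment is described, 10.3 does not agree with 10.1 as written, and the analysis has no clear period or sequence term. Equal counterbalancing does nothing about predictability.

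**Conclusion.** The point holds as a weakness in the stated rule and analysis; it does not show that the trial is biased. The rule for order would be satisfied by alternation, under which 95% to 97% of orders follow from one known order. That is a poor basis for a double-blind claim with a subjective outcome.

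The drift consequences are conditional:
- full bias only if 10.3 is followed for everyone;
- 40% of the drift at an unadjusted 14:6 split;
- no bias but a conservative test at 10:10.

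The error rates rest on N = 20, alpha 0.05, no carry-over and assumed period effects of 0.25 to 0.75 SD, none of which except N comes from the documents. Balancing the order does not deal with carry-over. Sections 5.0 and 7.0 refer to two scanning visits where 10.1 has one session, so what counts as a period also needs stating. The change should be made; it costs little.

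**What to change.** 1. **Section 10.1.** Replace the sentence on order with text such as: *Sequence (real-sham or sham-real) is assigned from a computer-generated balanced list in randomly permuted blocks. The list is held by a person who sets the device and does not collect ratings. Participants and staff who collect ratings do not have access to it.* Keep the block sizes in a restricted document, outside the protocol.
2. **Section 10.3.** State that the numbered list names the scan conditions and that the order of the two LIFUP scans follows the assigned sequence.
3. **Section 12.0.** Treat condition as a within-subject factor, add period and sequence terms, and define time. For one real-minus-sham difference per participant, this amounts to averaging the two sequence-group means, with N - 2 degrees of freedom (18 for 20 participants, 33 for 35).

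**Cost.** One list to generate and hold, someone not collecting ratings to set the device (a role the supplied text does not describe), and one or two degrees of freedom. No extra participants or measurements are needed.
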